9.3.2.1 Process evaluation data collection

Qualitative interviews will be conducted with a purposive sample of 60 patient participants in each of the two trial arms and up-to 30 of their carers. Sampling will ensure engagement of trial participants

with different ages and functional impairment. Interviews will take place after the 17-week assessment. Participants will be asked to consent to being contacted after their 17-week follow-up in the main PISC form. Consent will be re-affirmed prior to a semi-structured telephone interview by the qualitative researcher carrying out the process evaluation. Interviews will be audio recorded.

Semi-structured in-depth interviews will be conducted with 40 therapists delivering the enhanced rehabilitation programme (four from 10-12 sites), and will explore implementation from the therapists' perspectives. Interviews are expected to last a maximum of an hour and will be audio recorded. Interviews will be carried out at two time points: midway through therapists' anticipated involvement in the trial, and at the end of their involvement. The interviews will be carried out over the telephone at a convenient date and time.

Therapists will be asked to record key reflections using a critical incident technique. Data will be collected in the form of 'critical incident reports' which follow a reflective cycle. Therapists will be asked to complete these reports throughout their involvement in FEMuR.

In order to describe the extra rehabilitation therapy sessions, the visiting therapist will record the length and content of each session on a case report form. In order to describe the usual rehabilitation programme provided by the NHS patients will have patient-held diaries for visiting therapists to complete in order to record the number, length and content of usual rehabilitation care. Also whenever possible, routinely collected electronic data that therapists complete on their Therapy Manager system or its equivalent will be collected. The NHS IT manager will extract activity data, and send the pseudonymised to the qualitative researcher identifiable only by participant trial ID (randomisation number). The following will be extracted from these treatment logs and from the electronic records:

- Randomisation number
- Date of extra session
- Whether the session was face to face or indirect
- Where the face to face session was held
- If the session was face to face, how much time was spent on different aspects such as, physical exercises, activities of daily living (ADL) practice, working on the workbook
- When the sessions were given in patient's recovery timeline

Data from these records will be used to monitor participant adherence (e.g. missed or cancelled appointments), and therapist adherence to the trial protocol. In addition, as part of the health economic data collection we will ask all patient participants to record health service and admissions data along with concomitant medication use on the CSRI collected at baseline and at 17 and 52 weeks' follow-up.

9.3.3 Patient Transfer

For patients moving from the area, every effort should be made for the patient to be followed-up at another participating FEMuR III trial site and for this trial site to take over responsibility for the patient. The CTRC should be notified in writing of patient transfers.

9.3.4 **Premature Discontinuation of Trial Intervention**

Patients may be withdrawn from treatment for any of the following reasons:

- The patient withdraws consent.
- Intercurrent illness preventing further treatment.
- Any change in the patient's condition that justifies the discontinuation of treatment in the clinician's opinion.

If a patient wishes to prematurely discontinue from trial intervention, sites should nevertheless explain the importance of remaining on trial follow-up.. Generally, follow-up will continue unless the patient explicitly also withdraws consent for follow-up (see section 9.3.5).

9.3.5 Withdrawal from Trial Completely

Patients or carer participants are free to withdraw consent at any time without providing a reason. Patients who wish to withdraw consent for the trial will have anonymised data collected up to the point of that withdrawal of consent included in the analyses. The patient will not contribute further data to the trial. Data up to the time of withdrawal will be included in the analyses in accordance with the Data Protection Act 2018.

9.4 Trial Closure

The end of the trial is defined to be the date on which data for all participants are locked and data entry privileges are withdrawn from the trial database. However, the trial may be closed prematurely by the Trial Steering Committee (TSC), on the recommendation of the Independent Data and Safety Monitoring Committee (IDSMC).
10 SAFETY REPORTING

All safety events will be recorded by researchers when they are made aware of the event by the patient, carer, the treating clinicians, or therapists, in accordance with the principles of GCP. Safety event reporting information will be included in the training given to the therapy teams delivering the intervention and they will be given copies of the safety event reporting forms and details of how to enter them on to the trial database or send to the CTRC.

AE reports and SAEs not related to the intervention will be entered on to the remote data entry system at follow-up visits. SAE reports related to the intervention will be completed and sent to the CTRC within 24 hours of becoming aware of the event.

Safety events will be captured on two separate forms: Adverse Events form for all non-serious events and SAEs not related to intervention and a Serious Adverse Events (SAE) form for serious events related to intervention. The SAE form will have two sections, the first is for the healthcare professional to complete at site who will complete information including the seriousness of the event and whether it is related to the trial and return to the CTRC trial manager. The trial manager will liaise with the Chief Investigator (or agreed delegate) who will complete the second part of the form, including an assessment of expectedness for related events.

All SAEs, along with the PI's assessment of whether it is related to the intervention and for related events the CI's assessment of whether or not it is expected, will be reported to the REC annually. All SAEs which are assessed as related and unexpected will be reported to the REC and Sponsor in an expedited manner.

10.1 Definitions

There are different categories of safety events.

Adverse Event (AE)

An "Adverse Event" (AE) is any untoward medical occurrence in a participant, including events which are not necessarily caused by or related to the trial intervention. See section 10.2 for further guidance.

Related Adverse Event (related AE)

A "Related Adverse Event" (related AE) is an AE which has been assessed as having a causal relationship to the trial intervention (see section 10.5 below).

Serious Adverse Event (SAE)

A "Serious Adverse Event" is an AE which has been assessed as meeting the definition of "serious" (see section 10.3 below).

Related Serious Adverse Event (related SAE)

A "Related Serious Adverse Event" is an SAE which has been assessed as having a causal relationship to the study intervention (see section 10.5 below).

Related Unexpected Serious Adverse Event (RUSAE)

A "Related Unexpected Serious Adverse Event" is a related SAE which has been assessed as being unexpected (see section 10.6 below).

10.2 Notes on AE Inclusions and Exclusions

On this study AEs will include the following:

- Non-injurious falls;
- An exacerbation of a pre-existing illness;
- An increase in frequency or intensity of a pre-existing episodic condition;
- A condition (even though it may have been present prior to the start of the trial) detected after the start of the trial; and
- Continuous persistent disease or symptoms present at baseline that worsens during the trial.

The following will not be included as AEs:

- Medical or surgical procedures where the condition which leads to the procedure is the adverse event;
- Pre-existing disease or conditions present before treatment that do not worsen; and
- Overdose of medication without signs or symptoms.

10.3 Assessing "seriousness"

All safety events will be assessed for "seriousness". The assessment of "seriousness" should be made by the investigator responsible for the care of the participant using the following criteria. Events meeting the below criteria will be classified as "serious" (i.e. SAEs, related SAEs / RUSAEs). A safety event will be assessed as "serious" if it:

- Results in death;
- Is life-threatening (refers to an event during which the participant was at risk of death at the time of the event; it does not refer to an event which might have caused death had it been more severe in nature);
- Is a fall that results in injury and repeat fractures;
- Requires hospitalisation or prolongation of existing hospitalisation;
- Results in persistent/significant disability or incapacity;

• Other important medical events that, based upon appropriate medical judgement, may jeopardise the participant and may require medical or surgical intervention.

10.4 Notes on Severity / Grading of Adverse Events

The assignment of the severity/grading should be made by the investigator responsible for the care of the participant using the definitions below.

Regardless of the classification of a safety event as serious or not, its severity must be assessed according to medical criteria alone using the following categories:

Mild: does not interfere with routine activities **Moderate**: interferes with routine activities **Severe**: impossible to perform routine activities

A distinction is drawn between serious and severe events. Severity is a measure of intensity (see above) whereas seriousness is defined using the criteria in section 10.1, hence, a severe AE need not necessarily be a Serious Adverse Event.

10.5 Relationship to Trial Intervention

All safety events will be assessed for causality. The assignment of the causality should be made by the investigator responsible for the care of the participant using the definitions in table Table 1: Definitions of Causality. If any doubt about the causality exists the local investigator should inform the CTRC who will notify the Chief Investigator.

Only events related to trial intervention should be reported, events related to trial participation but not necessarily the intervention do not need reporting,

Relationship	Description	
Unrelated	There is no evidence of any causal relationship. N.B. An	
	alternative cause for the AE should be given	
Unlikely	There is little evidence to suggest there is a causal relationship	
	(e.g. the event did not occur at the time, or as a consequence of,	
	the rehabilitation intervention). There is another reasonable	
	explanation for the event (e.g. the participant's clinical condition,	
	other concomitant treatment).	
Possibly	Iy There is some evidence to suggest a causal relationship (e.g.	
	because the event occurred at the time, and may be a	
	consequence of, the rehabilitation intervention). However, the	
	influence of other factors may have contributed to the event (e.g.	
	the participant's clinical condition, other concomitant treatments).	
Probably	There is evidence to suggest a causal relationship and the	
	influence of other factors is unlikely.	
Almost certainly	There is clear evidence to suggest a causal relationship and other	
	possible contributing factors can be ruled out.	

Table	1: Definitions	of Causality
-------	----------------	--------------

In this study, only events which are assessed as "possibly", "probably" or "almost certainly" related will be classified as related events (i.e. related AEs / related SAEs / RUSAEs).

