3.4.2 Secondary Outcome/Endpoints

Secondary endpoints include:

Efficacy:

- 1. Anxiety and depression (HADS) ³⁶
- 2. Cognitive status (AMTS)³³
- 3. Hip pain intensity at (VAS) for hip pain intensity³⁷
- Falls self-efficacy (FES-I) (self-efficacy)^{38,39}
 Fear of falling (VASFoF)⁴⁰
- 6. Physical function (SPPB)^{49,50}
- 7. Grip strength⁴⁶

Carer behaviours may make an important contribution to the intervention's effectiveness. We will also include items to measure care tasks and roles in terms of the type of support provided and the number of hours spent providing support. We will ask about help with the workbook, goal-setting and the practice of rehabilitation exercises as well as more general assistance.

Carer of patient:

- 8. Care-giver strain (CSI)⁵¹
- 9. Care-giver anxiety and depression(HADS)³⁶

Safety:

- 10. Number of adverse events across the two arms
- 11. Number of serious adverse events across the two arms
- 12. Number of re-admissions to hospital following hip-fracture repair surgery

Health Economics:

- 13. Incremental cost-utility ratios, EuroQol EQ-5D-3L (three levels)⁴¹
- 14. Health service and personal social care Cost-utility, (CSRI)⁴³

Process Evaluation:

- 15. Refine the programme theory that was generated from the previous realist review when developing the intervention programme
- 16. Investigate therapists' expectations and experience of implementation, identifying the actual practices, likely tailoring and interactions that took place within the trial setting. Also, investigate therapists' skill level, relevant training, previous experience and level of familiarity of working in this sector. Finally, investigate therapists learning over time and its potential impact on outcomes.
- 17. Investigate the mechanisms driving and shaping the tailoring of the enhanced rehabilitation programme to individual patients and its possible impacts on outcomes.
- 18. Investigate trial participants' experiences and views about their involvement in the FEMuR trial.
- 19. Synthesize all data collected and link it to the explanation of trial findings in relation to the refined programme theory.

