9.2.1 Process for recording adverse events

All adverse events will be recorded (across both arms) by researchers when they are made aware of the event by the patient, carer, the treating clinicians, or therapists, in accordance with the principles of 'Good Clinical Practice'. Adverse event reporting information will be included in the training given to the therapy teams delivering the intervention and they will be given Instructions on how to enter adverse events on to the trial database. The adverse event form will be completed by investigators at site who will complete information including the seriousness of the event and whether it is related to the intervention. All adverse events will be presented to the Independent Data and Safety Monitoring Committee (IDSMC) periodically. Trial- serious related events will be reported to the CTRC within 24 hours of sites becoming aware. They will also be reported to the IDSMC Chair person and the research ethics committee periodically.

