10.8 Reporting Procedures

All safety events will be recorded and reported for each patient participant from the period of randomisation until their final 52 week follow-up assessment.

Depending on the nature of the event the reporting procedures below should be followed. Any questions concerning safety event reporting should be directed to the CTRC in the first instance.

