10.8.1 Non serious safety events (AEs / related AEs)

All such events, whether related or not, should be recorded on an Adverse Event Form and entered into the trial database (see section 10.2 for reportable events).

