10.9 Responsibilities – Site Principal Investigator

The site Principal Investigator is responsible for recording and reporting to CTRC all safety events that are observed or reported during the trial, regardless of their relationship to the trial. All serious events related to intervention (SAEs / related SAEs / RUSAEs) must be reported immediately by the investigator to the CTU on an SAE form. All other adverse events and serious adverse events not related to intervention should be reported on the regular progress/follow-up reports.

Minimum information required for reporting

- Trial randomisation number
- Sponsor trial number
- One identifiable coded subject
- One identifiable reporter
- A causality assessment
- I. The SAE form should be completed by a designated investigator, a physician named on the 'signature list and delegation of responsibilities log' as responsible for reporting serious safety events and making trial related medical decisions. The investigator should assess the event for the likelihood that it is a response to the trial intervention. In the absence of the designated investigator the form should be completed and signed by an alternative member of the research site trial team (as named on the delegation log) and submitted to the CTRC. As soon as possible thereafter the responsible investigator should check the SAE form, make amendments as appropriate, sign and re-send to the CTRC. The initial report shall be followed by detailed reports every 5 days until resolution.
- II. When submitting a SAE to the CTRC research sites should also telephone the appropriate trial co-ordinator on telephone number [name] to advise that an SAE form has been submitted.
- III. Send the SAE form by fax (within 24 hours or next working day) to the CTU:

[contact]

- I. The responsible investigator must **notify** their R&D department of the event (as per standard local governance procedures).
- II. The participant must be followed-up until clinical recovery is complete and laboratory results have returned to normal, or until the event has stabilised. Follow-up may continue after completion of protocol treatment if necessary.
- **III.** Follow-up information is noted on another SAE form by ticking the box marked 'follow-up' and returning to the CTRC as information becomes available. Extra, annotated information and/or copies of test results may be provided separately.

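### Section 10.5 restricts reporting to intervention-related events, against six other places in the protocol that require all events in both arms; a site following 10.5 would return incomplete AE and SAE counts that cannot be compared between arms

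*Protocol*

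**What the plan says.** Section 10.5, which deals with causality, contains this instruction: "Only events related to trial intervention should be reported, events related to trial participation but not necessarily the intervention do not need reporting".

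The sections on reporting set a different rule:

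- Section 10.8: "All safety events will be recorded and reported for each patient participant from the period of randomisation until their final 52 week follow-up assessment".
- Section 10.8.1, on non-serious events: "All such events, whether related or not, should be recorded on an Adverse Event Form".
- Section 10.8.2: SAEs unrelated to the intervention go into the trial database at the 17- or 52-week visit.
- Section 10.9: the site principal investigator must record and report every safety event "regardless of their relationship to the trial".
- Section 9.2.1: AE recording covers both arms.
- Introduction to section 10: the Adverse Events form carries non-serious events and also SAEs that are not related.

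Two safety endpoints in section 3.4.2 depend on this rule. Endpoint 10 is the "Number of adverse events across the two arms", and endpoint 11 is the same count for SAEs. Endpoint 12 is hospital re-admissions.

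**The concern.** Two instructions in the same chapter produce two different datasets. Under 10.8 and 10.9 each arm contributes all its events. Under 10.5 each arm contributes only events that an investigator attributes to the intervention.

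This matters because of what a two-arm count is for. When all events are counted, randomisation does the attribution: a difference between arms is evidence about the programme whatever anyone thought caused each event. When only related events are counted, the endpoint becomes a tally of causality judgements made by clinicians who know the allocation (section 8.6 says they cannot be blinded). Harm that nobody attributed to the programme would not be counted. A benefit, such as fewer falls in the intervention arm, could not show at all.

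The counts also go to the IDSMC, which advises on continuation (sections 9.2.1, 10.8.2 and 15.3.3).

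**Working it through.** The protocol gives no figure on this point and no arithmetic applies. The check is a comparison of texts.

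**1. Is the conflict explicit?** Yes. The first clause of the 10.5 sentence limits what is reported. Six places (9.2.1, the section 10 introduction, 10.8, 10.8.1, 10.8.2 and 10.9) require all events, and 10.8.1 and 10.9 expressly say that relatedness does not matter.

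**2. Is 10.5 consistent with itself?** No. It opens by requiring a causality assessment for every safety event. Its table has five grades, of which only the top three count as related. For the lowest grade, 'Unrelated', it asks that an "alternative cause for the AE should be given". If only related events were reported, the two lowest grades would never be used.

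**3. What would a site following 10.5 return?**

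| | All-events rule (10.8, 10.9) | Rule in 10.5 |
|---|---|---|
| Intervention arm | related and unrelated events | related events only |
| Control arm | all events | few or none |

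The control-arm entry follows from the protocol's own terms. The summary defines the intervention as the enhanced programme and the control as usual care. The schedule in section 9.1 footnotes the trial intervention as given only to those randomised to that arm. On this meaning a control participant cannot have an intervention-related event. The entry is 'few or none' rather than 'none' because section 8.6 also describes the trial as comparing two rehabilitation interventions. On that looser meaning some control events could be called related, but unrelated events would still be lost in both arms.

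**4. Does anything else point the same way as 10.5?** Two places, weakly.

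- The schedule in section 9.1 marks AE and SAE monitoring under the trial-intervention column, which its footnote confines to the intervention arm, and then at the 17-week visit, the qualitative interviews and the 52-week visit. Taken literally, monitoring between baseline and week 17 belongs to one arm.
- The visit descriptions in 9.1.3 and 9.1.5 name AEs and RSAEs but not unrelated SAEs. Those lists are stated not to be exhaustive.

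**5. Which endpoints are exposed?** Endpoints 10 and 11. Endpoint 12 is protected, because section 9.3.2.1 has all patient participants give admissions data on the CSRI at baseline, 17 and 52 weeks.

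**The case against.** The best defence is that 10.5 is one sentence against six consistent places, and that the data collection tools follow the six. The Adverse Events form is designed to take unrelated events, and site training covers safety reporting (section 13.4). The second half of the sentence contrasts the intervention with trial participation. Under a heading about relationship, it may have been meant only to define what counts as related. This argument stands as far as likelihood goes: most sites would probably report everything. It does not rescue the sentence, whose first clause is an instruction about reporting and is wrong as written.

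A reader might infer that the control count is zero by construction and the safety comparison void. The documents do not support that. It would require sites generally to follow 10.5 against the rest of the chapter, and it fixes one meaning of 'intervention' where the protocol uses two.

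A reader might also infer that, even with 10.5 corrected, the counts are biased against the intervention by a known amount, because "Adverse event reporting information will be included in the training given to the therapy teams delivering the intervention" and those teams make up to six extra visits. Unequal ascertainment is plausible, but its size cannot be derived. Six sessions is a maximum. Section 9.2.1 also lists patients, carers and treating clinicians as sources of reports. Many control patients will see usual-care therapists, though section 8.2 notes that in the feasibility trial some had no community rehabilitation. No capture rate is given for either arm.

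**Conclusion.** The contradiction is real and the 10.5 sentence should be corrected. Wherever it is followed, all unrelated events are lost and few or no control-arm events are reported, so endpoints 10 and 11 are incomplete and not comparable between arms or between sites working to different rules. The realistic harm is inconsistent reporting at some sites, of unknown extent, rather than certain loss of the comparison. The conclusion assumes only that at least one site takes the sentence at its word. The primary outcome and endpoint 12 are not affected.

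The documents do not support going further and restricting the safety endpoints to events elicited at the 17- and 52-week visits. That could miss events in patients who die, withdraw or lose capacity before a visit. The protocol cites 12-month mortality of 14-58%, plans on 79% retention, and stops data collection when capacity is lost (section 12.2). Setting aside events first reported by therapists could also undercount the intervention arm, since some of them would have come to light anyway.

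**What to change.** 1. **Section 10.5.** Delete the sentence or replace it with wording such as: 'An event is classed as related only if it is judged possibly, probably or almost certainly related to the enhanced rehabilitation programme. This classification decides which SAEs need 24-hour reporting. It does not limit recording: all AEs and SAEs in both arms are recorded and reported as set out in 10.8 and 10.9.'
2. **Schedule in section 9.1.** Move AE and SAE monitoring between baseline and week 17 out of the intervention-only column, or footnote it as applying to both arms. Name unrelated SAEs in 9.1.3 and 9.1.5 as well.
3. **Optional.** Add a source-of-report field to the AE form and describe the source by arm. Keep all recorded events in the main comparison, so that unequal ascertainment becomes visible without changing the endpoints.

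The cost is a wording amendment, a reminder to sites and, if step 3 is taken, one extra field and one descriptive table. Endpoints, sample size and the primary analysis stay as they are. It should be done before sites are trained. If any site has already worked to 10.5, its unrelated events should be sought retrospectively in both arms.

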9 PARTICIPANT TIME LINE, ASSESSMENTS AND PROCEDURES

9.1 Schedule for Follow-up

Participant follow-up visits should take place at 17 and 52 weeks post randomisation

Procedures	Screening	Baseline / Randomisation *	Trial intervention**	17 weeks post randomisation Follow-up	Qualitative interviews	52weeks post randomisation Follow-up
Eligibility screening and consent						
Assessment of eligibility criteria	Х					
Written and informed consent (patient / carer))	х					
Confirm consent		Х	Х	Х	Х	Х
Randomisation		Х				
Discharge data		Х				
Outcome measurement - patient						
NEADL		х		Х		Х
HADS		Х		Х		Х
AMTS		Х		Х		Х
VAS hip pain intensity		Х		х		Х
FES-I		Х		Х		Х
VASFoF		Х		Х		Х
EQ-5D-3L		Х		Х		Х
CSRI		Х		Х		Х
Grip strength		Х		Х		Х
SPPB				Х		Х
Outcome measurement - carer						
CSI		Х		Х		Х
HADS		Х		Х		Х
Trial Intervention**			Х			
Qualitative interviews						
Re-affirm consent verbally specifically for qualitative phone interview. (patient / carer)					х	
Qualitative telephone interview					Х	
Safety Event Reporting						
Monitoring of Adverse Events			Х	Х	Х	Х
Monitoring of Serious Adverse Events			Х	Х	Х	Х

* Randomisation and baseline should take place no later than 4 weeks after hip fracture repair surgery

** If randomised to intervention arm.

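### Section 10.5 limits reporting to intervention-related events, against sections 9.2.1, 10, 10.8 and 10.9, and section 10.6 labels expected events as RUSAEs

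*Protocol*

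**What the plan says.** Section 10.5, which deals with causality, contains the sentence "Only events related to trial intervention should be reported, events related to trial participation but not necessarily the intervention do not need reporting". The same section opens by requiring a causality assessment for every safety event, and its Table 1 has categories for unrelated and unlikely events.

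Other sections set a wider rule. Section 9.2.1 says "All adverse events will be recorded (across both arms) by researchers when they are made aware of the event". Section 10 says "AE reports and SAEs not related to the intervention will be entered on to the remote data entry system at follow-up visits". Sections 10.8 and 10.9 require all safety events to be reported, whether or not they are related.

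The safety endpoints in section 3.4.2 include "Number of serious adverse events across the two arms" and the matching count of adverse events. Neither is restricted to related events.

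On classification, section 10.1 says that a related SAE "is an SAE which has been assessed as having a causal relationship to the study intervention", and it defines a RUSAE as a related SAE judged unexpected. Section 10.6 says that serious related events on a short list (falls, fractures and other injuries during therapy sessions) are to be judged expected and classed as RUSAEs.

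**The concern.** Site staff hold two opposite written instructions on which events to report. The choice between them is not neutral between arms. The footnote to the schedule in section 9.1 attaches the trial intervention to participants "If randomised to intervention arm", so a usual-care participant's event could hardly be rated as related to it. A site that applied 10.5 literally would drop unrelated events in both arms and nearly everything in the control arm. The by-arm counts would be incomplete and lopsided, and the intervention would look less safe than it is.

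The 10.6 error concerns a different safeguard. RUSAE status decides which events go to the REC within 15 days. A rule that gives that label to expected events contradicts the definition on which the route depends, and it gives no instruction for a related SAE that is not on the list.

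**Working it through.** The protocol gives no figure that could be reproduced on this point, so the check is a comparison of the text.

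**Step 1: what is to be captured or reported?**

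| Section | Rule | Verb | Limited to intervention-related? |
|---|---|---|---|
| 10.5, disputed sentence | Participation-related events exempt | reported | Yes |
| 10.5, opening and Table 1 | Causality rated for every event, including unrelated ones | assessed | No |
| 9.2.1 | All AEs in both arms; all presented to the IDSMC | recorded, presented | No |
| 10 | All safety events; AEs and unrelated SAEs entered at follow-up visits | recorded, entered | No |
| 10.8 | All safety events, randomisation to 52 weeks | recorded and reported | No |
| 10.8.1 | All non-serious events, related or not | recorded, entered | No |
| 10.8.2 | Unrelated SAEs at 17 or 52 weeks; all serious events to the REC annually and to the IDSMC periodically | entered, reported | No |
| 10.9 | The site principal investigator's duty covers all events | recorded and reported | No |

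The disputed sentence stands alone. Sections 10.8 and 10.9 contradict it in the same verb. Sections 9.2.1, 10, 10.8.1 and the database-entry rule in 10.8.2 conflict with it to the extent that a site takes an event that need not be reported as one that need not be entered.

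**Step 2: what follows if 10.5 is obeyed literally?**

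- Unrelated and participation-related events are omitted in both arms.
- In the enhanced arm, events attributed to the rehabilitation sessions survive.
- In the usual-care arm almost nothing can qualify, if the intervention means the enhanced programme, as the section 9.1 footnote indicates.
- The endpoints in 3.4.2 count all events, so both arms are undercounted, the control arm more.

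The size depends on the share of sites that follow 10.5 and on the event rates. The protocol gives neither.

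**Step 3: 10.6 against 10.1.**

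- 10.1: serious + related + unexpected = RUSAE.
- 10.6: serious + related + on the list = expected = RUSAE.

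Both cannot hold. Section 3.2.5 already names injury or falling during therapeutic exercise as a possible risk, which supports reading the list as one of expected events. The RUSAE label is then the slip. Section 10.8.2 sends RUSAEs to the REC within 15 days, so 10.6 as written puts the listed events on that route. Unlisted related SAEs belong there only by virtue of 10.1, because 10.6 does not mention them.

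**Step 4: wording on relatedness.**

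Section 9.2.1 says that trial-related "serious related events will be reported to the CTRC within 24 hours of sites becoming aware", in a sentence whose words appear out of order. Section 10 describes the SAE form as going to a healthcare professional "who will complete information including the seriousness of the event and whether it is related to the trial". Sections 10.1, 10.5 and 10.8.2 tie relatedness to the intervention. The two usages differ for an injury caused by a research assessment. The Short Physical Performance Battery (SPPB), given by the researcher to both arms at 17 and 52 weeks, is the clearest case.

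**The case against.** The best defence is that the sentence sits in the causality section and was probably meant to say which events count as related, not which are captured. The Table 1 categories for unrelated and unlikely events make sense only if such events are collected. There is also a real difference between recording and reporting: sections 9.2.1 (for all AEs) and 10.8.1 speak of recording, and the endpoints could be counted from database entries even if nothing were reported. Sites are also trained on safety reporting (section 13.4). These points make it less likely that sites will follow 10.5 literally. They do not remove the conflict, because 10.8 and 10.9 use the word reported and the 10.5 sentence carries no limit to classification. Central data queries (section 13.2) concern data requested or entered, and would not readily reveal an event that was never entered.

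A reader might infer more in two places.

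- **Loss of the control arm's safety data.** At 1:1 allocation 446 / 2 = 223 participants are in usual care, and one could say that all of them would have almost no reportable event. That is a worst case. It needs every site to prefer one sentence to all the contrary sections. It also needs the intervention to mean the enhanced programme only, whereas sections 3.2.5, 8.6 and 11.4 use the word for both arms. On that wider reading unrelated events would still be lost, but the imbalance between arms would be less certain.
- **A gap for SPPB injuries.** One could say that a serious injury during the SPPB escapes expedited reporting. The text is inconsistent on this, not silent: 9.2.1 can be read as a 24-hour rule for trial-related serious events. Under 10.8 and 10.9 such an injury is recorded and reported in any case, and under 10.8.2 it reaches the REC annually and the IDSMC periodically. The protocol gives no injury rate, and confining relatedness to the intervention may be deliberate. Whether to widen it is a choice of scope.

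**Conclusion.** Two stated rules give a wrong result if followed, and both should be corrected. The 10.5 sentence contradicts the protocol's own reporting rules and puts the by-arm AE and SAE endpoints at risk at any site that obeys it. Section 10.6 contradicts the RUSAE definition and misdirects the 15-day route.

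The wording conflicts are certain. The bias is conditional on sites following 10.5, and its size cannot be derived from the protocol. Its direction, against the intervention, assumes that the trial intervention means the enhanced programme only. The inconsistent wording on trial-related and intervention-related events is a secondary point.

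**What to change.** 1. In 10.5, delete the sentence, or limit it to which events are classified as related. State that all AEs and SAEs are recorded and reported in both arms as in 10.8 and 10.9.
2. In 10.6, state that the listed therapy-session events are expected related SAEs and that any related SAE not on the list is a RUSAE.
3. Optional: bring 9.2.1 and the opening of section 10 into line with 10.1 and 10.8.2 on what an event must be related to, and say whether a serious injury during a trial assessment such as the SPPB takes the 24-hour and 15-day routes.

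Items 1 and 2 cost wording only. Under item 2 the listed therapy-session injuries leave the 15-day REC route that the present text could be read to give them; they keep the 24-hour report to the CTRC. If under item 3 the sponsor chose to count assessment injuries as related, causality guidance, forms and site training would need matching changes, and a few more events might be classed as related.
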